4.15 Subgroup Analysis

Subgroup analyses (especially for the analysis of the primary endpoint) will be considered for the categories of OA at baseline (unilateral, bilateral), country, and infusions received group (received all infusions, missed one or more infusions) from the mITT Analysis Set who have a baseline and at least one post-treatment WOMAC pain subscale score available.

4.16 Safety Analyses

Safety will be assessed by adverse events, laboratory assessments (including pharmacokinetic data), vital sign measurements, ECG data, index knee examination, X-Ray and MRI (including but not limited to Minimum Joint Space Width (mJSW) and Incidence of Rapidly Progressive Osteoarthritis (RPOA) Types I and II), and physical examination abnormalities using the Safety

LEVI-04-21-02 Statistical Analysis Plan	Version: Final 3.0
Date: 18-Mar-2024	Page 26 of 34

Analysis Set.

4.16.1 Plasma Concentration Analyses

Summaries for concentrations will be presented for the Safety Set by LEVI-04 dose using descriptive statistics (number of participants, mean, SD, CV %, median, minimum, and maximum). Concentration values below the limit of quantification (BLQ) will be treated as 0 when calculating summary statistics. Where all values are BLQ, the mean, median, minimum, and maximum concentration will be presented as BLQ and the SD and CV % will be reported as not applicable.

4.16.2 Adverse Events

An AE is defined as "any untoward medical occurrence in a participant administered a pharmaceutical product, regardless of causal relationship with this treatment". An AE can therefore be any unfavorable and unintended sign (including an abnormal laboratory finding), symptom, or disease temporally associated with the use of a medicinal product, whether considered related to the medicinal product or not. For surgical or diagnostic procedures, the condition/illness leading to such a procedure is considered as the AE rather than the procedure itself.

An event will be considered a treatment-emergent AE (TEAE) if the start or worsening of the event was on or after the administration of IP. Summaries of adverse events will be limited to TEAEs, but listings of all events will be provided. A serious adverse event is an event recorded as 'Serious' on the adverse event eCRF page. Adverse events will be classified by MedDRA SOC and PT.

The overall summary of TEAEs will include frequencies and percentages and will be presented for the following:

- Overview of adverse events;
- All adverse events by SOC and PT;
- Serious adverse events by SOC and PT;
- Adverse events of special interest by SOC and PT;
- Adverse events by SOC, PT, and severity;
- Adverse events related to study treatment by SOC and PT

Relationship to study drug will be classified as "unrelated" or "related". The severity of an adverse event will be rated by the investigator as "mild", "moderate", or "severe". Participants experiencing multiple instances of the same PT are only counted once within each SOC and PT combination. Participants experiencing multiple instances of the same PT will only be counted

LEVI-04-21-02 Statistical Analysis Plan	Version: Final 3.0
Date: 18-Mar-2024	Page 27 of 34

once according to the highest severity during the treatment emergent period when summarizing severity.

Serious adverse events, if present, also will be listed using verbatim, SOC, and PT. Should any serious adverse events occur during the study, the serious adverse events are displayed in a table and a narrative for each serious adverse event included in the study report.

4.16.3 Vital Signs Measurements

Vital sign observed values and changes and shifts from Baseline will be summarized at each scheduled visit, where applicable. A listing of all clinically significant abnormal results will be presented.

4.16.4 Clinical Laboratory Tests

Clinical laboratory parameters, including observed values and changes and shifts from Baseline, will be summarized at each scheduled visit, where applicable. Laboratory parameters may be classified as low, normal, or high (quantitative parameters) or abnormal or normal (qualitative parameters) by the central laboratory according to the reference ranges provided in the laboratory data transfer. Low, high, and abnormal results will be flagged in the listings of individual participant data. Some parameters may not have normal ranges.

4.16.5 ECGs

The overall ECG interpretation will be summarized by presenting the number and percentage of participants with "Normal", "Abnormal, not clinically significant", and "Abnormal, clinically significant". Shifts from Baseline in overall ECG interpretation will also be presented. A listing of all clinically significant abnormal overall ECG interpretations will be presented.

Continuous ECG parameter (e.g., QTcF) observed values and changes from Baseline will be summarized per schedule.

4.16.6 Physical Examinations

Physical examinations will include, at a minimum, assessments of the cardiovascular, respiratory, gastrointestinal, neurological, and musculoskeletal systems. Any abnormal findings will be recorded as medical history or adverse events depending on the time of assessment.

LEVI-04-21-02 Statistical Analysis Plan	Version: Final 3.0
Date: 18-Mar-2024	Page 28 of 34

4.16.7 X-Rays

Minimum Joint Space Width as determined by X-Ray will be summarized by observed values and changes from Baseline at Visit 11 The incidence of Rapidly Progressive Osteoarthritis (RPOA) will be summarized.

5. DATA HANDLING

5.1 Baseline and Study Visits

The last non-missing value, including unscheduled, prior to the first dose of study drug will be used as the Baseline value. Summaries presented by nominal collection day and/or by time point will be based on the schedule of assessments as planned in the protocol and as recorded on the eCRFs.

5.2 Pooling of Sites

Sites contributing less than 16 participants to the PP Analysis Set will be pooled. Pooling will begin by sorting the sites based on the number of participants in the PP Analysis set. The site with the lowest number of participants will be pooled with the site with the next lowest number of participants. If necessary, pooling with subsequent sites will continue until the pooled site contains at least 16 participants in the PP Analysis set. Pooling for additional sites will continue until all sites/pooled sites have at least 16 participants in the PP Analysis set. Pooled site will be used for all analysis (e.g., ANCOVA) containing site in the model or site as a stratification factor.

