4.5 Analysis Sets

The Intention-to-Treat Analysis Set

The Intent-to-Treat (ITT) Analysis Set will include all participants randomly allocated to a treatment, based on the intention to treat "as randomized" principle (i.e., the planned treatment regimen rather than the actual treatment given in case of any difference).

Modified Intention-to-Treat Analysis Set

The Modified Intention-to-Treat (mITT) Analysis Set will include all participants from the ITT Analysis Set who have a baseline and at least one post-treatment WOMAC pain subscale score assessment available.

Per-Protocol Analysis Set

The Per-Protocol (PP) Analysis Set will include all participants from the mITT Analysis Set who have been treated according to the trial protocol and fulfill the following criteria:

- Absence of major clinical trial protocol deviations with respect to factors likely to affect the efficacy of the treatment.
- Adequate compliance with trial medication: participants must have at least four study drug administrations, including an administration at Week 16.

Protocol deviations will be reviewed prior to unblinding to determine which, if any, participants are to be excluded from the Per-Protocol Analysis Set.

Safety Analysis Set

The Safety Analysis Set will include all participants who have been administered at least one dose of trial treatment. Participants will be analyzed according to the actual treatment they receive.

LEVI-04-21-02 Statistical Analysis Plan	Version: Final 3.0
Date: 18-Mar-2024	Page 17 of 34

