4.11 Primary Endpoint Analysis

The primary population of all efficacy analyses will be the ITT Analysis Set. The change from baseline in WOMAC pain subscale score will be analyzed using an ANCOVA model with main effect treatment and covariates study center and baseline score. The primary timepoint for analysis will be week 17. Since an interim analysis is to be performed, the final analysis will be conducted between each of the three treatment arms and placebo using a simple combination test (1/2 weight on interim Z and 1/2 weight on final Z) in order to maintain the overall specified alpha level. Further, p-values will be adjusted (and compared to 0.05) using a step-down Dunnett testing method for comparison of the three active doses with placebo.

The step-down testing method will first apply Dunnett adjustment for three comparisons (0.3 mg/kg, 1.0 mg/kg, and 2.0 mg/kg LEVI-04) with placebo. If the lowest adjusted p-value is non-

LEVI-04-21-02 Statistical Analysis Plan	Version: Final 3.0
Date: 18-Mar-2024	Page 20 of 34

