7. INTERIM ANALYSIS

An interim analysis (IA) will be conducted on the first 208 randomized participants in the study. The interim analysis will be performed once all 208 participants have completed the Week 5 visit or have discontinued prior to Week 5. Based on the IA's conditional power analysis, the study will continue as planned with a total of 416 participants randomized, or with an increase of up to 208 participants (an additional 50%) up to a total of 624 participants. Conditional power calculations will be performed using two alternative methodologies:

1. Multiple imputations will be utilized to impute missing data. The Week 17 effect size will be determined for each imputation. The conditional power will be calculated based on these multiple imputations interim Week 17 effect sizes. The Week 17 effect size for the

LEVI-04-21-02 Statistical Analysis Plan	Version: Final 3.0
Date: 18-Mar-2024	Page 31 of 34

- post-interim participants will be assumed to be from the same distribution as its associated Week 17 effect size estimate from the interim participants.
- 2. Multiple imputations will be utilized to impute missing data. The Week 5 effect size will be determined for each imputation. The conditional power will be calculated based on these multiple imputations interim Week 5 effect sizes. The Week 5 effect size for the post-interim participants will be assumed to be from the same distribution as its associated Week 5 effect size from the interim participants

A single set of one hundred imputations will be determined and utilized for both methods above.

The IA summary will be shared with the IA independent statistician. Below is the mock summary of the IA:

LEVI-04-21-02 Statistical Analysis Plan	Version: Final 3.0
Date: 18-Mar-2024	Page 32 of 34

Page 1 of 1 DDMMMYYYY **DRAFT** program.sas

Levicept Ltd.: Protocol LEVI-04_21_02 Table 1 Interim Analysis

Summary of Mean Change from Baseline in WOMAC Pain Subscale Score and Associated Conditional Power Intent-to-Treat Analysis Set – Multiple Imputations

	0.3 mg/kg (N=xx)	1.0 mg/kg (N=xx)	2.0 mg/kg (N=xx)	Placebo (N=xx)
Method 1: Change from Baseline to Week 17	1	1		
n	XX	XX	xx	XX
LS Mean (SE) ^a	xx (xx.x)	xx (xx.x)	xx (xx.x)	xx (xx.x)
LS Mean Difference (SE) ^a	xx (xx.x)	xx (xx.x)	xx (xx.x)	
Method 2: Change from Baseline to Week 5				
N	XX	xx	xx	xx
LS Mean (SE) ^a	xx (xx.x)	xx (xx.x)	xx (xx.x)	xx (xx.x)
LS Mean Difference (SE) ^a	xx (xx.x)	xx (xx.x)	xx (xx.x)	
Conditional Power ^b	 			

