Method 1				
Final planned sample size (N=416)			XX.X	
50% increase in final sample size (N=624)	XX.X			
Method 2				
Final planned sample size (N=416)	xx.x			
50% increase in final sample size (N=624)	XX.X			

- a: From an ANCOVA model with main effect treatment and covariates study center and baseline score with missing scores imputed using multiple imputations methodology. For method 1, participants that are still in study without week 17 data will be considered as missing at random. For both methods 1 and 2, for participants who discontinued due to lack of efficacy of adverse event, imputation will be done using the placebo as the treatment group.
- b: Conditional power is calculated as the probability for at least one of the comparisons against placebo is significant at the Dunnett adjusted type-1 error of 0.xxx per comparison (controlling overall type-1 error at a two-sided 0.05 level), assuming the post-interim effect size comes from the same distribution as its associated interim effect size.

LEVI-04-21-02 Statistical Analysis Plan	Version: Final 3.0
Date: 18-Mar-2024	Page 33 of 34

The two methods of estimating the effect size and consequently, the conditional power could lead to different sample size reassessments. The independent statistician will report the most conservative (largest) sample size in the recommendation to the designated personnel at Levicept. The only recommendation communicated to Levicept will be whether the sample size will need to increase or stay the same.

Conditional Power Calculations

For each of the methods above, conditional power will be calculated as follows:

1. Z_{ii} , i = 1,2.3 will be calculated by transforming the interim p-value of each dose group

comparison to placebo using the inverse normal transformation of the ANOVA t-statistics.

2.
$$\delta_i = Z_{i1} \sqrt{\frac{1}{i} + \frac{1}{i}}$$
, $i = 1,2,3$ is the effect size of the three dose group comparisons to

placebo from the interim participants, which is assumed to be also the effect size of the post-interim participants.

$$\rho_{ij} = \lambda_{i \ j}, \lambda_{i} = \sqrt{\frac{ni1}{ni1 + n01}}$$

LEVI-04-21-02 Statistical Analysis Plan	Version: Final 3.0
Date: 18-Mar-2024	Page 34 of 34

4. Let Λ be a lower triangular matrix from the Cholesky decomposition of Σ .

 X_1 Let $X = (X_2)$ be a three-dimensional vector of independent standard normal random X_3

variables and let

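### SAP 5.2 pools sites on Per-Protocol counts for ITT models; at the interim most participants cannot yet be Per-Protocol, so about 15 sites shrink to about 3–5 center levels, a small loss of precision

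*SAP*

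**What the plan says.** SAP 5.2 sets the pooling rule: "Sites contributing less than 16 participants to the PP Analysis Set will be pooled". Sites are sorted by PP count and merged from the smallest upward until every site or pooled site has at least 16 PP participants. The result applies everywhere: "Pooled site will be used for all analysis (e.g., ANCOVA) containing site in the model or site as a stratification factor".

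SAP 4.11 names a different population for efficacy: "The primary population of all efficacy analyses will be the ITT Analysis Set".

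SAP 4.5 ties PP membership to events after randomization. On compliance, "participants must have at least four study drug administrations, including an administration at Week 16". On deviations, "Protocol deviations will be reviewed prior to unblinding to determine which, if any, participants are to be excluded from the Per-Protocol Analysis Set".

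SAP section 7 defines the interim cohort: "An interim analysis (IA) will be conducted on the first 208 randomized participants in the study". Its timing is: "The interim analysis will be performed once all 208 participants have completed the Week 5 visit or have discontinued prior to Week 5". The mock interim table is labelled as an ITT analysis, and its footnote a describes the estimates as "From an ANCOVA model with main effect treatment and covariates study center and baseline score". Protocol 10.1 and 10.4.8 add that about 80 participants will have completed Week 17 by then. SAP 4.3 and section 7 do not repeat that condition.

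Neither document gives a separate pooling rule, or a way of determining PP membership, for the interim.

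**The concern.** Two things do not fit together.

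First, the rule relies on a set that is largely undetermined when the interim is run. A participant between Weeks 5 and 16 cannot satisfy the Week 16 criterion, and no interim deviation review is described. A programmer following SAP 5.2 must either count only those already past Week 16, which merges most sites, or improvise. The interim ANCOVA supplies the Z-values, effect sizes and conditional power that decide between 416 and up to 624 participants, so this step should be fully specified in advance.

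Second, at the final analysis a covariate of the ITT model is grouped according to dropout, compliance and deviations, all of which arise after randomization and may depend on treatment. Counts of randomized participants avoid this.

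**Working it through.** **Inputs.** Threshold 16 (SAP 5.2). Interim cohort 208 (SAP 7). About 80 with Week 17 data (Protocol 10.1). About 15 sites (Protocol, Investigators and Trial Sites). Planned N 416, SD 19.2, dropout 15% (SAP 4.3). Randomization not by center (SAP 4.2).

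**Assumptions, not in the documents.** Up to 90 participants past Week 16, allowing for those between Weeks 16 and 17. As few as 80 × 0.85 = 68 PP participants after exclusions. Site counts from 12 to 20, with equal or uneven recruitment.

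**1. The plan's own figures.** With 104 × 0.85 = 88.4 evaluable per arm, the two-sided Dunnett critical value for three comparisons is 2.349 (0.0188 per comparison), as stated. Power for at least one significant arm comes to 90.6%, 87.6% and 87.8%, against the stated 90%, 88% and 86%. The design inputs are therefore read correctly.

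**2. Who can be PP at the interim.**
- With 80 past Week 16: (208 − 80)/208 = 128/208 = 62% cannot be PP.
- With 90: (208 − 90)/208 = 118/208 = 57%.
- Possible PP participants per site: 80/15 = 5.3, well below 16. Randomized per site: 208/15 = 13.9.
- Upper limit on levels: 80/16 = 5.

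**3. Levels left by the SAP 5.2 algorithm.** Means over 2,000 simulated sets of site counts, 15 sites:

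| Counts used | Equal sites | Uneven sites |
|---|---|---|
| Interim, 80 PP | 4.0 | 3.9 |
| Interim, 208 randomized | 9.5 | 8.6 |
| Final, 416 × 0.85 = 354 PP | 14.5 | 11.3 |
| Final, 416 randomized | 14.9 | 12.0 |

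Across 68–90 PP participants and 12–20 sites, the interim PP rule gives about 3–5 levels. If all 208 had already passed Week 16 with 15% lost (177 PP), it would give about 8. At the final analysis the two rules differ by less than one level with 15 sites; with 20 equal sites the gap is about two (16.7 against 18.6).

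**4. Cost in precision at the interim.** Let site explain a share r of the outcome variance, and let merging be unrelated to outcome, so that k levels out of K sites retain about (k − 1)/(K − 1) of it. Relative to keeping all sites separate,

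SE ratio = √{[1 − r(k − 1)/(K − 1)] / (1 − r)}.

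With K = 15 and k = 4:
- r = 0: 1.00
- r = 0.05: √(0.9893/0.95) = 1.020
- r = 0.10: √(0.9786/0.90) = 1.043

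The fairer comparison is with the roughly 9 levels that randomized counts would give. The denominator becomes 1 − r × 8/14:
- r = 0.05: √(0.9893/0.9714) = 1.009
- r = 0.10: √(0.9786/0.9429) = 1.019

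The fix therefore recovers about 0–2% of the interim standard error.

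**The case against.** The strongest reply is that little follows from this. Sites with few or no PP participants are merged, not lost, and the ANCOVA fits with four levels as well as with nine. Randomization is not by center, so coarser pooling should not bias the treatment contrast. The interim leads only to a recommendation to keep or increase the sample size; no efficacy stopping is described. SAP 4.9 has scores imputed again at the end and already warns that results for the interim cohort may then differ. All of this stands, and it keeps the point small.

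A PP threshold also has a use: it guarantees at least 16 per level in the PP sensitivity analysis and in the larger sets. Pooling on ITT gives that up. A site with 18 randomized would have about 18 × 0.85 = 15.3 in PP. The documents do not state this rationale, but the trade-off is real, if slight.

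Finally, the figure of 80 comes from the protocol alone. Under the SAP's Week 5 trigger, the number past Week 16 depends on the speed of enrolment.

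None of this supplies the missing instruction on how to pool at the interim, or a reason to group an ITT covariate by a post-randomization set.

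**Conclusion.** The point holds as a minor one. Taken literally, SAP 5.2 reduces about 15 sites to about 3–5 center levels at the interim, where randomized counts would leave about 9. The cost is an interim standard error up to about 4% larger than with all sites separate, or up to about 2% larger than under randomized counts, if site explains no more than 10% of the variance. That passes into the effect sizes and conditional power. Neither document states a conditional-power cut-off, so the chance of a changed sample-size decision cannot be computed. At the final analysis the number of levels barely changes with 15 sites; the remaining objection there is one of principle.

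A reader might infer more than the documents support:
- **That the center factor cannot be built at the interim.** This is true only in the sense that no interim PP determination is described. A factor with several levels can be formed and the model fitted.
- **That the treatment estimate is biased.** Nothing shows this, and randomization independent of center argues against it.
- **That dropout decides which sites are adjusted for.** Every participant is still adjusted for a site or a pooled site; only the grouping changes.

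The sizes rest on about 80 participants with Week 17 data, about 15 sites, and assumed recruitment patterns and site variance.

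**What to change.** In SAP 5.2, replace the PP Analysis Set with the ITT Analysis Set in all four places where it appears. Then add two statements:

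- The interim analysis pools sites on the 208 randomized participants.
- The final analysis pools sites once, on all randomized participants, before final unblinding, and uses that one pooling in both the stage-1 and stage-2 models.

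Interim and final pooling will still differ, because more participants will have been randomized by the end, but each will be defined in advance and free of post-randomization selection. The documents do not show whether the interim has been held. If it has, record the pooling actually used and apply the change to the final analysis.

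The cost is a short SAP edit, with no new data and no design change. The one downside is that some pooled sites may have slightly fewer than 16 participants in the PP sensitivity analysis.

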5.3 Missing Data

WOMAC pain scores will be imputed as described in Section 4.9 for the primary analysis based on multiple imputations. All other analyses will be based on available data. Handling of plasma values that are below the limit of quantification with respect to the pharmacokinetic analyses are described in Section 4.16.1.

5.4 Unscheduled Data

Unscheduled results will only be considered for Baseline determination; otherwise, unscheduled data will not be used in summary tables or included in the analyses. All unscheduled data will be presented in the listings.

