7.10 Laboratory Tests

7.10.1 Blood samples

All efficacy measures should be completed prior to blood draws to limit any potential influence of the procedure on the general perception of pain.

- Laboratory values for an analyte that is outside normal range per the central laboratory will be identified and may be repeated at the Investigator's discretion.
- Abnormal laboratory value(s) that the Investigator has evaluated as clinically significant and/or leads to participant withdrawal from the study will be recorded as an AE on the eCRF if the respective blood or urine sample was performed after administration of 1st dose IMP (Visit 3) and as Medical History otherwise.
- The Investigator will review all laboratory reports, evaluate the results, and confirm review by signing with date of review.
- All clinical laboratory tests are described in detail in the Laboratory Manual.

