7.11 Electrocardiogram (ECG)

Standard 12-lead ECG evaluations, reporting Ventricular Rate, PR-, QRS, QT-, and QTcF intervals will be collected as per Schedule of Events. ECGs will be interpreted centrally with a report provided to Investigator of potential findings, that will be noted as 'abnormal not clinically significant' or 'abnormal clinically significant'. The Investigator should include the report ECG findings in their overall assessment of eligibility based on medical history, symptoms and clinical findings on physical exam. ECGs can be repeated at the discretion of the Investigator.

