7.13 MRI Assessment

MRI of both knees to be performed prior to Randomization (Visit 3) in due time to allow for a central read and confirmation of eligibility prior to Randomization. The imaging technical requirements are explained in the Imaging Guidance Overview that will be provided to all sites. MRI images will be evaluated by an independent central reader. Specifics of the exact imaging procedures will be provided in the Imaging Charter. The central reader will provide a report including potentially relevant findings for eligibility assessment. The main consideration in the evaluation of eligibility and selection of Target knee based on the MRI reading is as described for the radiographic reading (see Section 7.12). It is recommended that data collected from the Diary Run-In period has been evaluated centrally for eligibility prior to MRI of both knees. A Follow-up MRI of Target Knee to be conducted at Visit 11 (Follow-up visit/EOT) +/-3 days. MRIs may be performed at other times during the study if indicated, as agreed with the Independent Adjudication Committee.

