4. STATISTICAL METHODOLOGY

4.1 General Principles

All collected study data will be presented in listings. All derivations and statistical analyses will be performed using SAS® software Version 9.4. Prior and concomitant medications will be coded using the current version of the World Health Organization (WHO) Drug Dictionary available at the start of the study and will be used for the duration of the study even if a newer version of the dictionary is released. Similarly, adverse events (AEs) and medical history will be coded using the current version of the Medical Dictionary for Regulatory Activities (MedDRA) available at the start of the study and will be used for the duration of the study.

Unless stated otherwise, descriptive summaries for continuous variables will include n (number of participants with non-missing results), mean, standard deviation (SD), median, minimum, and

LEVI-04-21-02 Statistical Analysis Plan	Version: Final 3.0
Date: 18-Mar-2024	Page 14 of 34

maximum. For categorical variables, n and percent will be provided. Percentages will be calculated out of the number of participants in the given population with a non-missing result.

Nominal outcome summaries, presented by collection day and/or by time point, will be based on scheduled assessments as planned in the protocol. Unscheduled assessments will be presented in listings and will not be included in the analyses except for determination of Baseline as described in Section 5.1. All other visit and time point collections will be as recorded on the electronic case report forms (eCRFs).

WOMAC subscale scores will be standardized to a range of 0 to 10. Imputation of missing WOMAC pain subscale scores described in Section 4.9 will be based on the original score range. Standardization will occur after imputation at the time of analysis. Listings will present the original scores.

The primary analysis will be conducted once data collection associated with this analysis has been completed. That is, no additional data will be collected that would affect the results of the primary analysis despite the study being ongoing.

Unless otherwise stated, hypothesis testing will be two-sided with an alpha level of 0.05.

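### The SAP's exclusion of unscheduled results has no exception for participant-level safety incidence, so an RPOA case seen only on for-cause imaging could be missing from the imaging-based RPOA count and that count could disagree with the AESI table.

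*SAP*

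**What the plan says.** SAP 5.4 applies one rule to every data type: "Unscheduled results will only be considered for Baseline determination; otherwise, unscheduled data will not be used in summary tables or included in the analyses". It then adds: "All unscheduled data will be presented in the listings". SAP 4.1 repeats the rule: "Unscheduled assessments will be presented in listings and will not be included in the analyses except for determination of Baseline". In 4.1 the sentence follows one about summaries by collection day or time point. In 5.4 no such limit is given.

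The protocol expects unscheduled safety results. Section 7.13 says: "MRIs may be performed at other times during the study if indicated, as agreed with the Independent Adjudication Committee". Section 7.10.1 allows laboratory values outside the normal range to be repeated, and section 7.11 says of ECGs: "ECGs can be repeated at the discretion of the Investigator".

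On joint safety, SAP Table 1 (like protocol Table 2) makes the incidence of joint events, including RPOA types 1 and 2, a safety endpoint. SAP 4.16 lists X-ray and MRI, including RPOA incidence, as an assessment alongside adverse events. SAP 4.16.7 ties minimum joint space width to Visit 11 and then says: "The incidence of Rapidly Progressive Osteoarthritis (RPOA) will be summarized". It does not say whether the cases come from scheduled images, all images or adjudication.

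**The concern.** RPOA is the risk that the protocol's scientific rationale names for anti-NGF antibodies, and joint safety is one of three stated safety objectives. For-cause images are obtained because something about a joint has raised a question. A rule that keeps the routine image and sets aside the for-cause one can lower the incidence of the event that the imaging is there to detect.

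The SAP would also produce two counts of the same risk by different routes. One is the image-based incidence in 4.16.7, to which 5.4 applies on its face. The other is the table of adverse events of special interest (AESIs), to which it does not. Nothing in the SAP says how the two are to be reconciled. A reader of the study report who finds different RPOA counts would not know which is the endpoint.

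**Working it through.** The plan states no figure on this point, so the check is to follow a for-cause joint finding through each table in which it could appear.

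1. **Scheduled post-dose imaging.** The Schedule of Events and protocol 8.5.1 place it at Visit 11 (Week 20) or the early end-of-trial visit: radiographs of both knees, hips and shoulders, and MRI of the Target Knee only. Visit 12 (Week 30) is a telephone call.

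2. **When a finding would rest on for-cause imaging alone.** This needs an unscheduled image that shows the event and no scheduled image that also shows it. Examples are a participant who never has Visit 11 or end-of-trial imaging, a joint replaced before that imaging, an event after Week 20, or a finding visible only on MRI in the non-target knee.

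3. **Imaging-based RPOA incidence (SAP 4.16, 4.16.7).** This is a summary table. Under the literal text of 5.4 an unscheduled image cannot contribute to it, so the case is not counted.

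4. **Adverse-event tables (SAP 4.16.2).** Protocol 9.1.9 lists RPOA types 1 and 2, subchondral insufficiency fracture, osteonecrosis, acute fracture or bone marrow infiltration, and joint replacement as AESIs, and sends joint-safety events to adjudication. SAP 4.16.2 defines treatment emergence by onset or worsening relative to dosing, not by visit, and tabulates AESIs. The same case should be counted here.

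5. **Listings.** Under 5.4 the unscheduled result is listed.

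Steps 3 and 4 can therefore give different counts for one participant, with the imaging count the lower.

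**Size of one omitted case.** With 1:1:1:1 allocation, and taking every randomised participant as dosed:
- planned size: 416 / 4 = 104 per arm; 1 / 104 = 0.96 percentage points
- increased size: 624 / 4 = 156 per arm; 1 / 156 = 0.64 percentage points

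These are the effects of a single omission. They do not estimate how many omissions there would be. The documents give neither the frequency of for-cause imaging nor an expected RPOA rate.

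**Laboratory tests and ECGs.** Unscheduled repeats are also left out of the by-visit and shift summaries. Where a scheduled abnormal value prompts the repeat, that value stays in the table. Protocol 9.1.2 recognises that a repeat may be normal, and it requires laboratory, vital-sign and ECG findings judged clinically significant to be recorded as adverse events.

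**The case against.** The strongest reply has four parts.

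- **Harm is already tabulated.** A reader might infer from 5.4 that for-cause results are left out of the safety tables altogether. The documents do not support that. The listed joint events are AESIs, adjudicated and tabulated by onset, clinically significant test results become adverse events, and all unscheduled data are listed. This part stands, and it limits the point to the measurement-based summaries.
- **The rule may be meant only for by-visit summaries.** The context in 4.1 suggests so, and the RPOA sentence in 4.16.7 names no visit. But 5.4 covers summary tables and analyses without that limit, and 4.16 treats image-based RPOA as separate from adverse events. If the narrower meaning is intended, the SAP should say so.
- **The scenario is narrow.** Protocol 5.4.1 requires every effort to bring early leavers back for the Visit 11 procedures, and protocol 7.12 includes replaced joints in the follow-up radiographs. Protocol 7.13 foresees extra MRI, whereas 4.16.7 is the X-ray section. This makes omission uncommon but not impossible, since 4.16 joins X-ray and MRI in its RPOA item.
- **Repeat tests do not systematically show harm.** This stands. A reader might infer that dropping repeat laboratory tests and ECGs hides the worst results, but a repeat can equally be the reassuring one.

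**Conclusion.** The point holds in a limited form. As written, SAP 5.4 and 4.1 can remove an RPOA case seen only on for-cause imaging from the incidence in 4.16.7, while the same case should remain in the AESI table and the listings. The imaging count would then be too low and would disagree with the AESI count.

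This rests on reading 5.4 literally, on there being no usable scheduled image of the event, and on the finding being recorded as an adverse event as protocol 9.1.9 expects. One case moves an arm's rate by 0.96 percentage points at 104 per arm or 0.64 at 156 per arm. With rare events a single case could be a large share of an arm's count in that table. A reader might go on to say that a large part of the safety signal is lost, or lost more in one arm than another. The documents do not support either step: they give no event rate and no frequency of for-cause imaging by arm, and the AESI table still holds the case.

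Safety is summarised without inference (protocol 10.4.7), so no test or decision rule is affected. It is still worth correcting before the tables are produced, because the rule bears on a stated safety endpoint and a short change to the SAP settles it.

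**What to change.** Limit the exclusion in SAP 4.1 and 5.4 to summaries presented by visit or time point. Add to 4.16.7 that the incidence of RPOA and other joint events is counted per participant from all post-dose imaging, scheduled or unscheduled, with cases taken from the joint-safety adjudication so that the count agrees with the AESI table.

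The cost is SAP wording and minor programming. No new data are collected and the primary analysis is untouched. Event counts may be slightly higher than under the literal rule. Tables of worst post-baseline laboratory values or ECG interpretation could also be added, but they are new displays, optional, and not needed for this fix.
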